2.7.1.6 Duration of Complete Remission

Duration of Complete Remission (DOR) is the time from the date of the first documented CR to the date of first documented relapse from CR or death due to any cause, whichever occurs first.

The start date is the date of first documented CR and the end date is defined as the date of the first documented relapse from CR or death due to any cause. Duration of CR for Subjects without event will be censored at the date of their last adequate response assessment.

DOR will be analyzed using the Kaplan-Meier method. Estimates of the 25th, median and 75th percentile of the DOR and their 95% confidence intervals will be provided, Kaplan-Meier curves will be produced, if applicable.

- DOR applies only to subjects who have CR (responded).

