#### **12.5.1.6 Duration to Complete Remission**

Duration of Complete Remission (DOR) is the time from the date of the first documented CR to the date of first documented relapse from CR or death due to any cause, whichever occurs first.

The start date is the date of first documented CR and the end date is defined as the date of the first documented relapse from CR or death due to any cause. Participants continuing without event will be censored at the date of their last adequate response assessment.

DOR will be listed and summarized. Median duration and 95% Confidence interval will be reported.

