Response assessment will be performed by the investigator according to the assessment schedule depicted in protocol Table 8-1 based on available bone marrow assessment and peripheral blood every 3 cycles for core phase during the first 07 cycles and every 6 cycles for extension phase and all transfusions records as detailed in [Table 2-6](#) using the modified version of the published response criteria IWG for MDS. Moreover, response assessments can be performed at any time if clinically indicated, e.g. for confirmation of response but also for any suspicion of progression/relapse. These assessments are recorded as an unscheduled visit in the eCRFs and will be considered for the overall determination of response and progression/relapse with the respective assessment date.

The investigator does not determine best overall response, he/she is assessing only the response based on the given bone marrow and peripheral blood data, the history of transfusions and myeloid growth factor received within the last 2 weeks.

The best overall response (BOR) will be derived based on the CR secondary endpoint rules by Novartis as below:

- CR = at least one determination of CR without progression or relapse from CR within the four after CR.
- mCR = at least one determination of mCR (and not qualifying for a CR).
- PR = at least one determination of PR (and not qualifying for a CR/mCR).
- SD = at least one SD assessment and not qualifying for CR, mCR or PR.
- PD = progression after enrollment and not qualifying for CR, mCR, PR or SD.
- UNK = all other cases (i.e., not qualifying for confirmed CR or mCR or PR and without SD or progression).

Details on the definition of response categories which are to be captured in the eCRF by the investigator were defined in Table 8-2 of the protocol that was copied into Table 2-6 below.

Table 2-6 Modified response classification per IWG criteria in MDS

| Response category | Definition [#] |
|-------------------|-------------------------|
|-------------------|-------------------------|

| | |
|--|--|

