| Complete remission (CR) | 
Bone marrow: $\leq 5\%$ blasts with normal maturation of all cell lineages. (Note: Persistence of dysplasia will be noted but does not preclude achievement of complete remission [CR])
 
Peripheral blood
 
 1. Hgb ≥ 10 g/dL AND 2. Platelets $\geq 100*10^9/L$ AND 3. Neutrophils $\geq 1.0*10^9/L$ AND 4. Blasts 0% 
Note: the subject must not receive RBC or platelet transfusions, myeloid growth factor within 2 weeks before this disease assessment
 |
| marrow Complete remission (mCR) | 
Bone marrow: $\leq 5\%$ blasts and blast count decrease by $\geq 50\%$ compared to baseline
 
Peripheral blood/transfusion: Marrow CR may be achieved with or without improved blood counts or with or without transfusions
 |
| Partial remission (PR) | 
All CR criteria except
 
Bone marrow: $\geq 50\%$ decrease from baseline in blasts in bone marrow AND blast count in bone marrow $>5\%$
 |
| Stable Disease (SD) | Failure to achieve at least PR, but no evidence of progression for >8 weeks |
| Relapse from CR | 
Only in subjects with a CR:
 
At least 1 of the following criteria is met:
 
[In absence of another explanation not due to MDS, such as acute infection, bleeding, hemolysis, etc. Note that observation of peripheral blasts is not a sufficient criterion for relapse. However in that case, a bone marrow examination should be made to determine whether relapse has occurred.]
 
 • Return to baseline bone marrow blast percentage • Decrease of $\geq 50\%$ from maximum remission/response*** levels in neutrophils AND neutrophils $<1.0*10^9/L$. Note: neutrophils counts during periods of active infection will not be considered in determining the maximum • Decrease of $\geq 50\%$ from maximum remission/response*** levels in platelets AND platelets $<100*10^9/L$ • Decrease from maximum remission/response*** levels in Hgb concentration by ≥ 1.5 g/dL AND Hgb <10 g/dL • Becoming transfusion dependent** |

| | |
|----------------------------|---|

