| Disease progression | 
At least 1 of the following criteria is met:
 
[In absence of another explanation not due to MDS, such as acute infection, bleeding, hemolysis, etc. Note that observation of peripheral blasts is not a sufficient criterion for progression. However in that case, a bone marrow examination should be made to determine whether relapse has occurred.]
 
Bone marrow according to the number of blasts of the subject at baseline:
 
 1. Less than 5% blasts at baseline: $\geq 50\%$ increase in blasts over baseline to $>5\%$ blasts 2. 5%- $<10\%$ blasts at baseline: $\geq 50\%$ increase over baseline to $>10\%$ blasts 3. 10%- $<20\%$ blasts at baseline: $\geq 50\%$ increase over baseline to $>20\%$ blasts. Subjects with more than 20% of blasts will be considered to have transformation to acute leukemia per 2016 WHO classification (Arber et al 2016) 
Peripheral blood:
 
 1. Decrease of $\geq 50\%$ from maximum remission/response*** levels in neutrophils AND neutrophils $<1.0 \times 10^9/L$. Note: neutrophils counts during periods of active infection will not be considered in determining the maximum 2. Decrease of $\geq 50\%$ from maximum remission/response*** levels in platelets AND platelets $<100 \times 10^9/L$ 3. Reduction from maximum remission/response*** levels in Hgb by $\geq 2\text{g/dL}$ AND Hgb $<10\text{g/dL}$ 
Becoming transfusion dependent** Occurrence of acute leukemia or extramedullary leukemia per investigator's judgement
 |
|----------------------------|---|

| Modified Hematological Improvement per IWG-MDS criteria in MDS (Cheson et al 2006) | |
|---|---|
| HI category | Definition[#] (HI must last at least 8 weeks) |
| Erythroid response (HI-E) (pretreatment*, $<11\text{ g/dL}$) | 
 1. Hgb increase from baseline by $\geq 1.5\text{ g/dL}$, in at least 2 consecutive Hgb measurements and maintained over at least 8 weeks 2. Relevant reduction from baseline of units of RBC transfusions by an absolute number of at least 4 RBC transfusions/8 weeks compared with the pre-treatment transfusion number in the previous 8 weeks. Only RBC transfusions given for a Hgb of $<9\text{ g/dL}$ pre-treatment will count in the RBC transfusion response evaluation. |

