2.7.3 Handling of missing values/censoring/discontinuations

Missing data for safety and efficacy endpoints will not be imputed.

For the determination of CR, only assessments post enrollment and prior start of any other anti-neoplastic therapy or HSCT are considered.

For the determination of PFS events, only assessments post enrollment and prior start of any other anti-neoplastic therapy are considered. If disease progression/relapse from CR or death is documented after two or more missing response assessments, PFS will be censored at the last adequate response assessment prior to the event.

For PFS and duration of CR, an adequate response assessment is considered any disease assessment indicating response status apart from “unknown” or “not done”.

A subject whose disease has not progressed or died by the date of the analysis cut-off will have their PFS censored at the time of the last adequate tumor evaluation performed on or before the cut-off date. Clinical deterioration will not be considered as documented disease progression.

Further details were already described in [Section 2.7.1](#).

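### Duration of complete remission has no rule for a loss of remission recorded as disease progression, so it can be overstated and can contradict PFS

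*SAP*

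**What the plan says.** Duration of CR is the sixth secondary objective. In SAP 2.7.1.6 it starts at the first documented CR, and "the end date is defined as the date of the first documented relapse from CR or death due to any cause". For everyone else, "Duration of CR for Subjects without event will be censored at the date of their last adequate response assessment". Protocol 12.5.1.6 uses the same end events. Under SAP 2.7.3, "an adequate response assessment is considered any disease assessment indicating response status apart from" unknown or not done, so a visit recorded as progression is an adequate assessment.

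Elsewhere the SAP keeps progression and relapse apart. The PFS definition (SAP 2.7.1.2) lists disease progression including leukemic transformation, relapse from CR, and death as three separate events. The best-overall-response rule for CR asks for "at least one determination of CR without progression or relapse from CR", so it expects that either may be recorded after a CR. SAP Table 2-6 (copied from protocol Table 8-2) has one row for relapse from CR, restricted to participants with a CR, and another for disease progression, which is not restricted. Only the progression row contains "Occurrence of acute leukemia or extramedullary leukemia per investigator's judgement".

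No passage says how progression recorded in a participant in CR enters the duration of CR.

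**The concern.** The investigator enters the response category in the eCRF, and the end of CR is tied to a documented relapse. With two overlapping rows and no precedence rule, the label entered can decide whether the endpoint registers an event. The text steers leukemic transformation towards the progression label: Table 2-6, the PFS definition and the discontinuation criteria in protocol 9.1.1 all place it there. The clearest loss of remission is therefore the one most exposed to being missed.

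At stake is a descriptive estimate from a handful of responders. A remission that has ended could be counted as still running, and PFS and duration of CR could give different answers for the same participant at the same visit.

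**Working it through.** The documents state no figure for duration of CR, so there is none to reproduce. The check compares definitions, followed by an illustration of size.

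**1. Progression criteria against relapse criteria (SAP Table 2-6)**

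| Progression in a participant in CR | Relapse counterpart | Covered? |
|---|---|---|
| Marrow blasts up by at least 50% over baseline, past the stratum limit | "Return to baseline bone marrow blast percentage" | Yes: 1.5 × baseline is already at or above baseline |
| Marrow blasts at least 20% | Same | Yes: AML is excluded at entry, so baseline is below 20% |
| Neutrophil fall, platelet fall | Identical | Yes |
| Hemoglobin fall of at least 2 g/dL to below 10 g/dL | Fall of at least 1.5 g/dL to below 10 g/dL | Yes: the relapse threshold is looser |
| Transfusion dependence | Identical | Yes |
| Extramedullary leukemia | None | No |
| Acute leukemia by investigator judgement, without marrow or count relapse | None; peripheral blasts alone are stated to be insufficient for relapse | No |

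A grid check agrees. Of 168,280 baseline/current marrow pairs meeting progression, 0 failed the relapse criterion. Of 3,470 hemoglobin pairs, 0 failed.

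**2. What a literal derivation does**

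Take CR at C7D1 and progression or extramedullary leukemia recorded at C10D1. PFS has an event at C10D1. Duration of CR has none there, and three routes follow:
- No later assessment or death: censored at C10D1, the last adequate assessment.
- Later assessments: censored at the last of them, or an event when relapse is eventually recorded.
- Later death without a relapse record: an event at the death date.

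The first route is common by design, because extension-phase response assessments run until documented progression (protocol sections 3, 8.3 and 9.1.5). It is not universal: protocol 6.1.4.1 allows treatment and assessments beyond progression when there is no acute leukemia, and 9.1.1 keeps efficacy assessments going after most discontinuations. The first route is informative censoring. The others count time after progression as remission. All lengthen the reported duration.

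**3. Number of responders**

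Enrolled: 39 (SAP 1.1). The lowest and highest CR rates given for the two combination arms in protocol 4.3.2 are 10.5% and 33.3%. Expected CRs: 39 × 0.105 = 4.1 and 39 × 0.333 = 13.0, so about 4 to 13.

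**4. Illustration of size**

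Let CR durations be exponential with loss rate λ, and let a share f of losses be recorded as progression and censored on that date, with no later deaths. The hazard seen by Kaplan-Meier is λ(1 − f), so the median is multiplied by 1/(1 − f):
- f = 5%: 1.05
- f = 10%: 1.11
- f = 20%: 1.25
- f = 50%: 2.00

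With an assumed true median of 10 months, f = 10%, 25% and 50% give 11.1, 13.3 and 20.0 months.

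Now let a later death count as an event, as the SAP requires. With assumed median loss-to-death times of 3, 6 or 12 months and 18 to 24 months of follow-up after CR, simulation gives medians of about 10.4–10.9, 11.1–12.6 and 12.3–15.7 months.

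None of these shares, medians or survival times comes from the documents.

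**5. One case in a small sample**

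An invented set of eight durations (2, 4, 5, 6, 8, 9, 11, 12 months, all events) has a Kaplan-Meier median of 6, taking the first time the curve is at or below 0.5. Censor the ending at 4 months: the curve is 7/8 = 0.875 after 2, × 5/6 = 0.729 after 5, × 4/5 = 0.583 after 6, × 3/4 = 0.438 after 8. The median becomes 8. Censoring any one ending at or before 6 months has this effect; censoring one after 6 months leaves the median at 6.

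**The case against.** The best defence is that Table 2-6 already provides a relapse category reserved for participants in CR, met by any one criterion, and that it contains every marrow, count and transfusion criterion for progression. An investigator who applies the table as written should record relapse. On this view only extramedullary leukemia and leukemia without marrow or count relapse are left out, and the documents give no frequency for either. That stands as far as the criteria go. It does not supply a rule for the case where progression is the label entered, which the best-overall-response rule itself foresees.

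A second defence is that the consequence is limited. The endpoint is descriptive with no hypothesis test, and SAP 2.7.1 calls for a by-subject listing of response assessments, PFS events and duration of CR, so a mismatch would be visible. That stands as well, but a listing does not correct the Kaplan-Meier estimate.

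A third is that relapse or death is the prespecified end event in both documents, and that the current SAP addendum, made after database lock, was written to bring endpoints into line with the protocol. This is a fair reason to make any change openly.

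**Conclusion.** The gap is real and narrow. For marrow, count and transfusion progression it is one of recorded label; for extramedullary leukemia, or acute leukemia called without marrow or count relapse, it is one of definition. Where it bites, the direction is certain: duration of CR is too long and disagrees with PFS. With about 4 to 13 expected CRs, a single case can move the median. The actual size is unknown and may be zero.

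A reader might infer two stronger claims that the documents do not support. One is that any progression after CR is censored on the progression date. The rule censors only participants without an event, at the last adequate assessment, which can be later, and a later death is an event. The other is that the reported median could double. That needs an assumed 50% of losses recorded as progression and no later deaths; counting deaths as events brings the illustrated median from 20.0 down to about 12.3–15.7 months. The factor 1/(1 − f) is therefore best read as an upper illustration under exponential durations.

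**What to change.** In SAP 2.7.1.6, state that for participants with a CR the duration ends at the earliest of relapse from CR, disease progression (including transformation to acute or extramedullary leukemia) or death, and that progression recorded after a CR is derived as loss of CR on the PFS event date. Either make the same change in protocol 12.5.1.6 or list it in SAP section 4 as a change to protocol-specified analyses.

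Label the change as made after database lock and report how many participants with a CR it affects. If the number is zero, the estimate does not change and the report can say so.

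The cost is a sentence of text and a small programming change, using data already collected. The downside is that reported CR duration may be shorter, and that this is a documented post-lock change to a descriptive secondary endpoint.

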2.7.1.7 Time to Complete Remission

Time to Complete Remission is defined as the time from the date of enrollment (cycle 1 day 1) to the first documented CR.

Time to complete remission will be analyzed using the Kaplan-Meier Product-Limit method. Subjects who are known to be without CR will be censored at study-maximum follow-up time (i.e. Last Subject Last Visit (LPLV) for final analysis, for analysis of cut-off date min (LPLV, Cut-off date)) for subjects with a PFS event (i.e. disease progression or death due to any cause), or at the date of the last adequate assessment for subjects without a PFS event. Estimates of the 25th, median and 75th percentile of the time to CR and their 95% confidence intervals Kaplan-Meier plots will be provided, if applicable. Improvement in RBC/platelets transfusion independence

The number and percent of subjects who are RBC/platelets transfusion independent after the date of enrollment as per IWG-MDS will be provided.

RBC/Platelets transfusion independence rate is defined as the proportion of subjects having received <0 units (no RBC/Platelets transfusions) during at least 8 consecutive weeks after enrollment ([Table 2-6](#)). The number and percentage of subjects will be shown for the overall FAS and then also in only those with transfusion dependence at baseline. Percentages will be provided with exact 95% Clopper-Pearson confidence intervals. Bar graphs will be provided.

For subjects with at least one period of transfusion independence post-baseline, the total duration of all transfusion independence periods (which all individually must be at least 8 weeks) will be also summarized.

The duration of each period of transfusion independence is defined from the end date of the last transfusion received until the date transfusions are given again or last date of treatment administration in case transfusions had not (re-)started during treatment. The total duration of all transfusion independence periods is the sum of each period of the transfusion independence.

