## 1 Introduction

### 1.1 Background

It is estimated that 15,000 to 20,000 new cases of Myelodysplastic Syndromes (MDS) are diagnosed annually in the USA ([Klepin 2016](#)). The incidence of MDS is more frequent in male patients and increases with age, with a median age at diagnosis of about 70 years. MDS correspond to a heterogeneous group of hematopoietic diseases that are associated with impaired bone marrow function, ineffective hematopoiesis, elevated bone marrow blasts and persistent peripheral blood cytopenias. Cytogenetics abnormalities are frequently present at time of diagnosis. Patients with MDS have a predisposition to developing acute myeloid leukemia (AML) ([Heaney and Golde 1999](#)). Although progression to AML can frequently lead to death in patients with MDS, many deaths are consequences of cytopenias and marrow failure in the absence of leukemic transformation. To account for disease heterogeneity, assess the risk of progression to AML and estimate survival, MDS prognostication systems have been proposed. Prognosis is usually determined using the revised International Prognostic Scoring System (IPSS-R), which considers the percentage of bone marrow blasts, the number of cytopenias, and bone marrow cytogenetics. Patients with untreated MDS are stratified into five IPSS-R prognostic risk categories: very low, low, intermediate, high and very high, with median survival times of 8.8, 5.3, 3.0, 1.6 and 0.8 years, respectively and with 25% AML transformation rate of NR (not reached), 10.8, 3.2, 1.4, 0.73 years respectively ([Greenberg et al 2012](#)). In a large database of MDS patients (n = 7,012) distribution of patients across the 5 IPSS-R risk categories were as follows: Very low (19%), low (38%), intermediate (20%), high (13%) and very high (10%) ([Greenberg et al 2012](#)). Current treatment guidelines for MDS recommend modification of the disease with hematopoietic stem cell transplantation (HSCT, treatment with a curative intent), hypomethylating agents (HMA: azacitidine or decitabine) or intensive chemotherapy ([Fenaux et al 2014](#)). Choice of therapy is mainly driven by the IPSS-R score, the overall general health status and clinical assessment of comorbidities. For patients eligible for intensive therapy, and for whom a donor is available for HSCT or for whom the marrow blast count requires reduction, intensive chemotherapy may be considered ([Steensma 2018](#)). HSCT remains the only curative option for MDS patients; however, many MDS patients are not candidate for HSCT ([Passweg et al 2011](#); and see [Section 4.3.1](#)). In MDS patients without major co-morbidities who are classified as intermediate, high, very high risk by IPSS-R, and who do not qualify for HSCT or intensive chemotherapy, HMAs remain the first-line reference treatment. HMAs (azacitidine or decitabine) are generally administered for a minimum of 6 cycles (repeat cycle after 4 weeks), and continued for as long as the patient benefits. HMAs (azacitidine or decitabine) have a similar safety profile. In clinical practice, bone marrow suppression is the most common adverse reaction in demethylation therapy, and is also the main reason for the dose-reduction or discontinuations of decitabine or azacitidine. Supportive care, including blood transfusions, is frequently required. HMAs have improved outcomes for patients with intermediate/high risk/very high risk MDS; especially for patients who are not candidates for intensive chemotherapy regimens or HSCT. However, despite these improvements, prognosis for patients treated with HMA remains poor. Complete Remission rate (CR) with azacitidine or decitabine in higher-risk (IPSS; intermediate- & high, IPSS-R; intermediate, high & very high) MDS is rare. CR rate has been shown to be 9% for decitabine and 17 % for azacitidine in pivotal trials ([Kantarjian et al 2006](#), [Fenaux et al 2009](#)). Other trials

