
reported CR rate in MDS patients ranging from 7% to 25% with azacitidine and from 9% to 35% with decitabine. ([Sauntharajah 2013](#)).

Zeidan et al reported that azacitidine and decitabine used in monotherapy lead to similar clinical effectiveness and safety profiles retrospective study identified patients diagnosed with MDS between 2004 and 2011 in the US (SEER-Medicare linked database) who received  $\geq 10$  doses of either HMA for comparing clinical effectiveness in daily practice of azacitidine versus decitabine. Azacitidine was used for treating approximately 80% of the patients (n = 2,025). Survival from HMA initiation was estimated with Kaplan-Meier methods and adjustment was made for relevant covariates. No significant survival difference was found between azacitidine and decitabine in MDS patients, including in MDS patients with excess of blasts. However, it cannot be ruled out treatment outcome of a novel compound given in a combination regimen may vary with nature of the partner drug

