Preliminary efficacy data reported in study [PDR001X2105] with higher risk MDS participants are showing high response rates. At the time of the latest analysis (cut-off: 10-Apr-2020), in the MBG453 + decitabine arm, 11 of 18 (61.1%) evaluable high risk and very high risk MDS patients have achieved a response (6 complete remissions [33.3%], 3 marrow complete remissions [16.7%], 2 stable diseases with hematologic improvement [11.1%]). Median of exposure in this arm is approximately 8 months. Durability of response and clinical benefit is being observed with the longest responding higher-risk MDS subjects continuing on study for more than 30 months. In the MBG453 + azacitidine arm, 11 of 19 (57.9%) evaluable higher-risk MDS patients have achieved a response (2 complete remissions [10.5%], 7 marrow complete remissions [36.8%], 2 stable diseases with hematologic improvement [10.5%]). Of note, data from this arm is less mature with duration of follow-up of approximately 3 months. Rationale for combining MBG453 (sabatolimab) with HMA (IV/ SC azacitidine and IV/ oral decitabine)

Despite the fact that single-agent HMAs are available for the treatment of patients with higher risk MDS, alternative treatment strategies are urgently needed; because achieving complete remission with HMA alone in this difficult to treat population is a rare event and the duration of the clinical benefit is commonly transient. Furthermore, attempts to use HMA single-agent to increase the HSCT rate or as alternative treatment of cytarabine in higher risk MDS patients have been disappointing. In addition, many higher risk MDS patients eventually progress on HMAs and ultimately progress to AML.

Combining HMAs with novel agents may improve their clinical efficacy and overcome resistance. The fact that immune checkpoint inhibitors have been able to generate deep and durable response in various cancers including hematologic malignancies together with emerging preclinical and clinical data (see [Section 15](#)) strongly supports the evaluation of the novel anti-TIM-3 antibody MBG453 (sabatolimab) combined with HMAs in MDS.

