#### **12.5.1.7 Time to Complete Remission**

Time to Complete Remission is defined as the time from the date of enrollment to the first documented CR.

Time to complete remission will be analyzed using the Kaplan-Meier Product-Limit method. Patients who are known to be without CR will be censored at the last adequate assessment. Estimates of the 25th, median and 75th percentile of the PFS and their 95% confidence intervals will be provided, if applicable.

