A total of 39 subjects were enrolled in this study. Subjects were recruited from sites within the United States. No pre-treatment stratification is planned. The investigator or designee must ensure that only subjects who meet all the inclusion and none of the exclusion criteria are enrolled in the study.

There are 4 types of periods/phases: Screening phase, core phase, extension phase and post treatment safety follow-up

Screening phase: A signing of written informed consent obtained through day 1 of enrollment (from up to 28 days of period prior to core phase start date).

[figure not shown]
Core phase: A 12 months of treatment period is a **core phase**

Extension phase: Extension phase for efficacy and/or survival status (up to 24 months of last subject enrolling) or in addition to core phase (12 months), an additional 12 months of treatment period is **extension phase**.

Post treatment safety follow up: Post treatment safety follow-up monitoring for adverse events (AEs) for 30 days following the last dose of azacitidine or decitabine or INQOVI (oral decitabine), or 150 days following the last dose of MBG453 (sabatolimab), whichever is later.

Figure 1-1 Study design

Study design

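### The time-to-CR curve censors non-CR subjects who switch therapy or are transplanted as if they could still reach CR, so it plateaus above the CR rate; the planned median and 75th percentile are very unlikely to be reached

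*SAP*

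**What the plan says.** SAP 2.7.1.7 defines time to CR from enrollment to first documented CR and analyses it by Kaplan-Meier. The planned output is "Estimates of the 25th, median and 75th percentile of the time to CR and their 95% confidence intervals", plus Kaplan-Meier plots, where applicable. No summary restricted to subjects with CR is planned.

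Non-CR subjects are censored in one of two ways. Those with a PFS event are censored at study-maximum follow-up; the rest are censored earlier, "or at the date of the last adequate assessment for subjects without a PFS event". Protocol 12.5.1.7 had one rule for everyone: "Patients who are known to be without CR will be censored at the last adequate assessment".

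Three other SAP rules bear on who falls in the second group:

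- **2.7.3:** "For the determination of CR, only assessments post enrollment and prior start of any other anti-neoplastic therapy or HSCT are considered".
- **2.7.1.2:** PFS is censored before the start of new anti-neoplastic therapy. Progression or death after HSCT still counts as a PFS event.
- **2.7.1.1:** for the CR rate, discontinuation, transplant or progression before response counts as non-response.

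On size, SAP 1.1 states: "A total of 39 subjects were enrolled in this study".

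**The concern.** A subject without CR who moves to new therapy can have no later CR under 2.7.3 and no PFS event under 2.7.1.2. That subject is sent to the early-censoring branch. Kaplan-Meier then treats the subject as someone who would have gone on to CR at the same rate as those still followed. The same applies to a transplanted subject with no later PFS event. The curve and the CR rate would then disagree on the same 39 subjects, with the curve on the favourable side. SAP section 4 drops sensitivity analyses, so no planned output would show the gap.

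The second issue is the choice of summary. A curve over all subjects levels off near the CR proportion. If that is well below one half, the median and 75th percentile do not exist, and secondary objective 7 is left with the 25th percentile at best, a plot, and no numerical summary among responders.

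**Working it through.** **Inputs.** N = 39. The documents state no figure for time to CR, so there is none to reproduce. CR rates cited for HMA alone or sabatolimab + HMA:

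- Protocol 1.1, pivotal trials: "CR rate has been shown to be 9% for decitabine and 17 % for azacitidine in pivotal trials".
- Protocol 1.1, other trials: "reported CR rate in MDS patients ranging from 7% to 25% with azacitidine and from 9% to 35% with decitabine".
- Protocol 4.1: 15% (first-line HMA) and 12% (oral decitabine).
- Protocol 4.3.2: 6/18 = 33.3% (with decitabine) and 2/19 = 10.5% (with azacitidine).
- Protocol Table 1-4: 3/11 = 27.3% in higher-risk MDS at 800 mg Q4W.

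**Step 1: can the percentiles be reached?** Without early censoring, the curve ends at X/39, where X is the number of CRs. Reaching a percentile q needs X ≥ 39q, rounded up:

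- 25th: 9.75, so 10 CRs
- median: 19.5, so 20 CRs
- 75th: 29.25, so 30 CRs

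With X binomial (39, p):

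| CR rate p | P(X ≥ 10) | P(X ≥ 20) | P(X ≥ 30) |
|---|---|---|---|
| 7% | 0.03% | < 1e-6 | < 1e-6 |
| 12% | 1.5% | < 1e-6 | < 1e-6 |
| 17% | 11.4% | about 1e-6 | < 1e-6 |
| 25% | 52.4% | 0.04% | < 1e-6 |
| 27.3% | 65.1% | 0.13% | < 1e-6 |
| 33.3% | 88.4% | 1.5% | 3e-8 |
| 35% | 92.1% | 2.7% | 1e-7 |

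An even chance of reaching the 25th, median and 75th percentile needs a CR rate of about 24.6%, 50% and 75.4% respectively.

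**Step 2: a worked curve.** Take 7 CRs in 39, first seen as 3, 2, 1 and 1 at C4, C7, C10 and C13. Crude rate: 7/39 = 17.9%. Suppose 8 non-CR subjects switch or are transplanted without a PFS event, with 4, 2 and 2 censored just after C4, C7 and C10. The numbers at risk are 39, then 39 − 3 − 4 = 32, then 32 − 2 − 2 = 28, then 28 − 1 − 2 = 25.

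1 − (36/39)(30/32)(27/28)(24/25) = 1 − 0.801 = 19.9%

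Holding the same 8 in the risk set gives 1 − (36/39)(34/36)(33/34)(32/33) = 7/39 = 17.9%. With 8 censored in the same pattern, 5/39 = 12.8% becomes 14.0% and 13/39 = 33.3% becomes 37.7%.

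**Step 3: average excess.** The share affected is assumed. The simulation used 6,000 runs per cell and N = 39. CRs were split 40/30/20/10% over C4, C7, C10 and C13. For affected subjects, the last adequate assessment was spread evenly over baseline, C4, C7 and C10. Mean plateau minus mean crude rate, in percentage points:

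| Share of non-CR subjects affected | CR 12% | CR 17% | CR 25% | CR 33.3% |
|---|---|---|---|---|
| 10% | +0.6 | +0.8 | +1.1 | +1.3 |
| 20% | +1.3 | +1.7 | +2.3 | +2.8 |
| 40% | +2.9 | +4.0 | +5.2 | +6.4 |

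In the worked example, 8 of the 32 non-CR subjects is 25%, and the excess is 2.0 points, in line with the table.

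**The case against.** The case against has weight in several places.

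- **Progression and death are handled correctly.** The SAP already repairs the protocol's rule for the main competing events. A transplanted subject who later progresses or dies has a PFS event and stays in the risk set. The effect is also smaller if the last adequate assessment falls after HSCT. This stands and narrows the affected group. It does not reach switched subjects, whose PFS is censored before the new therapy.
- **The percentiles are conditional and a plot is planned.** A reader might infer that objective 7 will simply return a not-estimable result, or that no quartile can be reached. The documents do not support that. The 25th percentile is reached with probability 52–92% at CR rates of 25–35%, the plot shows timing in any case, and SAP 2.7.1 plans a listing of all response assessments.
- **Not every cited rate is low.** Protocol 1.1 reports CR, or CR with residual thrombocytopenia, in 10/20 (50%) with azacitidine + nivolumab and 8/21 (38%) with azacitidine + ipilimumab. Those are other checkpoint inhibitors, so the statement about unreachable percentiles is limited to HMA alone and sabatolimab + HMA.
- **The bias is small beside sampling error.** One subject is 1/39 = 2.6 points, and the exact 95% interval for 10/39 is 13.0–42.1%. The CR rate is reported separately under its own rules and is not read from this curve. This stands. The case for change is consistency between two outputs on the same subjects.
- **The two issues pull in opposite directions.** Early censoring makes a percentile easier to reach. At a 17% CR rate with 40% of non-CR subjects affected, the 25th percentile appears reached in 29% of simulations, against 12% on the crude proportion. That is itself a reason to correct the rule.

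**Conclusion.** The point holds in a limited form. The SAP's censoring rule for time to CR conflicts with its own rules on what can count as CR, and whenever such a subject is censored before a later CR in others, the curve overstates the CR proportion. The excess is about 0.6–2.8 points if 10–20% of non-CR subjects are affected. That share is an assumption, as are the timing of CRs and of the last assessments, so no fixed overstatement can be claimed.

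The median and 75th percentile are effectively unreachable at the cited 7–35% rates, ignoring early censoring. The 25th percentile is unlikely at 17% or below and has at least an even chance from about 25%.

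A reader might also infer that every discontinuation before CR should be a competing event, because 2.7.1.1 counts it as non-response. The documents do not support that for the curve: subjects who stop treatment without progression continue response assessments (Protocol sections 3, 8.3 and 9.1.5), and 2.7.3 bars CR only after HSCT or other anti-neoplastic therapy.

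The endpoint is descriptive, one of eight secondary objectives, and no hypothesis is tested. The change is worth making, but the study's conclusions do not turn on it.

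**What to change.** In SAP 2.7.1.7:

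1. Censor at study-maximum follow-up every non-CR subject who has a PFS event, starts other anti-neoplastic therapy or undergoes HSCT before CR. Censor all other non-CR subjects at the last adequate assessment. Cumulative incidence of CR with progression, death, HSCT and new therapy as competing events is the equivalent presentation, and gives the same curve when there is no other early censoring. Do not treat discontinuation alone as a competing event while response assessments continue.
2. Add time to CR among subjects with CR: n, median, minimum and maximum, and the number first in CR at C4, C7, C10 and C13.
3. Keep the percentiles, shown as not reached where that is the case.
4. Footnote any remaining difference between plateau and CR rate. It can arise from subjects lost to follow-up, from discontinued subjects counted as non-responders, and from the best-response derivation in 2.7.1.1, which requires no progression or relapse for a period after CR, whereas this endpoint uses first documented CR.

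The cost is SAP wording and one re-run table and figure, with no new data and no error-rate consequence. The curve becomes slightly less favourable. The SAP's document history places the current addendum after database lock, so this change must be labelled post-lock as well.
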